2. BACKGROUND AND SIGNIFICANCE

Bite splints and bruxism. Tooth wear is an extremely prevalent condition, with > 4 teeth per dentition showing significant wear in over 50% of the population, and the prevalence increases with age to 60% by the 7th decade of life (Cunha-Cruz et al., 2010). Moreover, patients who have a history of previous bite splint wear have higher rates of tooth wear (Cunha-Cruz et al., 2010), suggesting that early intervention and long-term splint wear are required to reduce the impacts of bruxism.

Bite splints and TMD. Recent evidence suggests that bite splint use is efficacious in reducing pain symptoms in TMD patients who have been wearing splints for 1 – 6 months; however, within 15 days of terminating splint use, symptoms return (Rehm et al., 2012). These authors conclude that terminating bite splint use in TMD patients is not recommended. If this is correct, then bite splints for TMD symptom management require long-term, perhaps permanent, use. Given that no oral devices are permanent and that custom acrylic orthotics are expensive to replace, there exists a need for an alternative that is feasible in terms of cost, reliability, and regular replacement.

Current standards. There are three recognized oral devices (Maeda et al., 2009), (1) a stock type, which does not adjust to an individual's dentoskeletal morphology, (2) the mouth-formed or boil and bite type and (3) the custom-made appliance. The first two types are over-the-counter (OTC) devices. Bite splints for use with TMD and bruxism are most often custom-made. Either custom-made or the boil and bite type are most often used as mouth guards in contact sports.

Evidence varies as to which of the three oral devices is superior. Most experts presently recommend the custom-made mouth guards for sports purposes (Maeda et al., 2009). For sleep bruxism, custom-made hard acrylic or boil and bite night guards are apparently equally efficacious (Klasser et al., 2010). Finally, a review of RCTs indicates that hard acrylic orthotics were superior to soft appliances or repositioning appliances in managing TMD pain (Friction et al., 2010).

The issue with custom-made hard acrylic appliances is that they are expensive and cannot be repetitively covered by insurance. Hence, there is a need for an inexpensive, reliable and replaceable alternative that has the functional efficacy of the custom hard acrylic appliances. It is also clear that, for such a device to be a legitimate alternative, it must undergo the appropriate clinical trials (ADA report. Using mouthguards to reduce the incidence and severity of sports-related oral injuries., 2006; Centers for Disease Control and Prevention. Promoting oral health: interventions for preventing dental caries, oral and pharyngeal

cancers, and sports-related craniofacial injuries. A report on recommendations of the task force on community preventive services., 2001; Friction et al., 2010).

Planned studies will escalate as follows. The initial studies will involve performing a small RCT with 29 subjects in two groups (below). Subsequent future research will involve full-sized phase III trials of the SOVA night guard, while simultaneously developing a jaw function simulator. The technologies and insights developed from the simulator and phase III trials will provide solid methods for successful phase IV SOVA trials. Subsequently, the advances made with the SOVA studies will provide the necessary means for conducting phase III and IV trials of the SISU mouth guard device, which will take place under the hostile conditions attending contact sports. Of course, additional IRB approvals and funding will be required to pursue these future objectives.

3. METHODS AND STUDY DESIGNS

3.1 Subjects. Sample size estimations (**Table 1**) are based upon a recent review of RCTs for bruxism management, in which acrylic appliances were evaluated (see Appendix 2 in (Huynh et al., 2007)). The mean \pm 1 SD number of bruxism episodes per hour with an occlusal splint (the gold standard) was 3.97 ± 0.58 , and for a palatal splint, the mean \pm 1 SD was 4.45 ± 0.63 . Using these means and the higher SD (0.63), along with an $\alpha = 0.05$ and $\beta = 0.8$, I determined that a study would be sufficiently powered with sample sizes of 29 per group. Based on other Michigan studies, I have estimated recruitment, exclusion and attrition rates, which suggest an estimated initial screening sample size of 120 necessary to end up with 29 per group (**Fig. 1**). There will be two treatment groups: a group receiving supervised training in the fabrication of the SOVA night guard (SOVA) and a group receiving the Michigan custom-acrylic bite splint (MI BS). Two groups times 29 subjects per group equals 58 total needed for analysis (**Fig. 1**, bottom).

Table 1. Treatment (Tx) groups & sample sizes (N).

[figure not shown]
Tx	SOVA	MI BS
N	29	29

Care will be taken to match the randomized groups for age, ethnicity, gender and TMD signs/symptoms. Alternatively these will be modeled as nuisance variables if attrition rates create bias and/or there is a lack of sufficiently sized screening pools. Subject inclusion criteria will be: (1) adults, male or female, (2) clinical signs of dental wear, (3) report from significant others of nocturnal grinding and clenching noises from potential subject, (4) absence of outstanding dental and medical conditions, including cardiovascular disease, sleep apnea, and diagnosed sleep disorders, (5) full dentition sans 3rd molars, (6) no movement or neurological disorders, (7) no active orthodontics, (8) no outstanding or previous periodontal problems, (9) no removable prostheses, (10) no medication use with movement disorders as known side effects, (11) ability to follow instructions, (12) ability to report to the clinical laboratory at appointed times over the course of the study. The presence or absence of TMD joint noises or masticatory myalgia will be permitted; however, joint arthritides will not be permitted.

3.2 Project design.

Fig. 2 provides an overview of the project flow. Each aspect will be described below.

3.2.1 Screening. Candidates will undergo a screening to assess co-morbidities and to identify inclusion and exclusion criteria. Standard questionnaires and screening instruments include the Research

Diagnostic Criteria for TMD (TMD-RDC) (Dworkin and LeResche, 1992), Jaw Function Limitation Scale (JFLS) (Ohrbach et al., 2008), the TMD Pain Screener (Gonzalez et al., 2011), Measure of Symptoms Sleep Scale (MOS), Perceived Stress Scale (PSS). Additionally, a brief clinical exam will be performed to evaluate dental and medical health, including an intra-oral and extra-oral head and neck examination, heart rate and blood pressure. Subjects meeting the acceptance criteria will be randomly assigned to one of the two groups (**Table 1**) using stratified randomization procedures (Suresh, 2011). Subjects will then have alginate impressions taken, and impressions will be poured up in stone. The models will be used either to fabricate the MI BS or to assess SOVA appliances for fabrication efficacy.

3.2.3. Splint delivery. For the SOVA group, subjects will be asked to fabricate SOVA devices in the clinical laboratory while receiving feedback from trained and calibrated study ‘instructors’. Fabrication will proceed according to manufacturer instructions. Calibrated instructors will be blinded to the study’s objectives, as will subjects. A “Michigan” acrylic bite splint will be fabricated using standard clinical practice and checked for fit and quality on subjects assigned to the MI BS group.

3.2.4 Subjective fabrication assessment. Standardized questionnaires will be provided to participants and will cover issues of ease of fabrication, ease of instructions, and other related issues for the devices. Box scales will be used to evaluate items individually and separately.

3.2.5 Quantitative fabrication assessments. Four aspects of fabrication will be evaluated by investigators: (1) stability—does the device move independently of the maxilla and is the mandible stabilized by the device, (2) retention—does the device resist displacement, (3) tissue adaptation—how much spacing exists between the maxilla and the device and between the device and mandible, and (4) health of the teeth, gingival, tongue, palate and lips.

3.2.5a. Stability and retention will be quantitatively assessed with jaw movement (custom jaw tracking devices in conjunction with a MaxTraq motion analysis system [Innovision, Columbiaville, MI] and EMG [LabChart, ADInstruments, Colorado Springs, CO] data) and force sensors (T-scan, Tektronix, South Boston, MA). For position-stability assessment, maxilla, mandible and the splint will be simultaneously recorded from at least three sites each (to capture 6 degrees of movement freedom). Subjects will clench, grind, perform closed border movements and vacuous chewing (verified with EMG and force sensors). For retention assessment, subjects will perform a series of tests designed to dislodge the device, e.g., tapping, forced blowing, coughing, chewing on gum. Stability and retention indices will be created based on whether device movements vary independently of jaw movements and applied bite forces, and how force sensor output varies during dislodgement exercises. (Note, the force sensors will be placed between the device and the maxilla, so that reductions in sensor output will indicate that the device is being dislodged.) Deviations will be used to form standardized indices of stability and retention, with smaller values representing greater stability and retention.

3.2.5b. Tissue adaptation will be assessed by using a 3D laser scanner. The occlusal, facial and lingual surfaces of the upper arch will be scanned as will the inner surface of the night guards. An index of

[figure not shown]

Fig. 2. Overview of planned studies (see text).

adaptation will be developed based on the volumetric spaces separating the teeth from the device, using topological software. Smaller volumes will represent better tissue adaptation. Volumetric indices will be compared between devices via ANOVA or appropriate statistical methods.

3.2.5c Tissue health will be assessed via appropriate, standard methods currently used in cariology and periodontology clinical studies (Monse et al., 2012; Tirapellia et al., 2010). Baseline measurements will be compared with post-device wear measurements. Between-group differences will be studied with a repeated measures ANOVA or appropriate statistical methods.

3.2.6 Compliance assessment. Compliance assessments will focus on: (1) how often the device is worn, (2) whether the device is removed at inappropriate times during the night, (3) whether alternative devices are used. Compliance will be assessed via subject self-report (daily log), nocturnal EMG recording devices and microwear methods. Subjects would be blinded to the purpose of the technological methods. Occlusal microwear patterns are unique to the surfaces against which occlusion occurs, and the microwear changes on a daily basis (Ungar et al., 2003). Hence, microwear assessment provides definitive evidence regarding splint compliance.

3.2.7 Functional efficacy. Two questions will be addressed under functional efficacy: (1) does the device alter bruxing activity, and (2) how do the teeth and device hold up under bruxing activity. Some of the technology used for compliance assessment, above, can be used here. 'Gold standard' methods for evaluating bruxing activity rely on polysomnography (PSG) and EMG activity; therefore, it will be important to employ these technologies for purpose of peer-review publications. To address the second question, how do the teeth hold up, 3-D laser scanning technology will be used to measure changes in macroscopic tooth structure, and confocal microscopy and scale-sensitive fractal analysis will be useful for addressing microwear.

3.2.8 User satisfaction. This will be assessed through a series of standardized questionnaires adopted from other clinical studies, e.g., the Oral Health Impact Profile (Slade and Spencer, 1994), the Tampa Scale for Kinesiophobia: TMD (Visscher et al., 2010), the TMD pain screener (Gonzalez et al., 2011). Questionnaires used in the SISU field tests (SISU mouthguards preliminary results), as well as forced choice, box scales and statistical methods developed in another study (Lin, 2008; Lin et al., 2013) will also prove useful for assessment of patient satisfaction. Also such questions as, does the device hurt or pinch anywhere, does your bite feel 'off' when you first remove the guard, how often do you take out the splint before the night is over, do you experience excessive salivation or dry mouth, do you ever wake up with the splint out for unknown reasons, does the device build up plaque and other deposits through time, do you ever just feel like not wearing it and if so why not, will be used to assess specific aspects of user satisfaction.

Table 2. Summary of objectives, methods and when performed		
Assessment	Method or modality (equipment)	When
Subjective fabrication	Questionnaires (na)	Step 2
Stability	Performance during jaw function, bite force and muscle use (MaxTraq + EMG + T-Scan)	Steps 2, 4, 5
Retention	Shape conformity (3-D laser scanner, topology)	Steps 4,5
Tissue adaptation	Tooth wear and gingival health (standard dental)	Steps 4,5,6
Tissue health		
Compliance	Self-report (questionnaires), Evidence of nocturnal use (EMG-sleep + microwear)	
Functional efficacy	Bruxism/TMD evidence, dental changes (EMG-sleep + 3-D scanning + microwear)	
User satisfaction	Questionnaires (na)	

3.2.9 Repeated measures (Step 4 Week 1 check-up and Step 5 4 Month check-up). Compliance, stability, retention, tissue adaptation and health, functional efficacy and user satisfaction will be assessed two times, viz., 1 week after delivery and 4 months after delivery (Fig. 2, Table 2). This will provide a

rigorous data set, reduce subject attrition and thus allow for both publications and further proposal applications to be pursued.

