4. STATEMENT OF COLLABORATION AND TIMELINE OF ACTIVITIES

Table 3. Timeline

Task	Sp/Su	F	W	Sp/Su	F	W
IRB						
Screening and recruitment						
Splint fabrication and first week						
Follow-up 4 months						
Analysis and Publication						

Table 3 estimates the timeline for the proposed studies. Each cell represents one month, with years being stratified into trimesters (Spring/summer, Fall, Winter). Based on clinical studies performed on TMD subjects at MICHRS and current projects assessing jaw function, I estimate that screening can be completed in 14 months. Actual participation can begin upon receiving IRB approval and identification of appropriate candidates. Studies involve subjects for 6 months. Accounting for lag times involved in stratified randomization, enrollment will probably lag by 1-4 months, indicating that studies will wrap up after 2 years as shown, with enrollment finalized by early fall of the 2nd year, and all follow-ups being completed during the Winter of the 2nd year. The final trimester will be heavily devoted to analysis and publication. Obviously, preliminary analyses (not shown) will begin as soon as data are available (approximately mid-Fall of year 1) in order to assure that experimental procedures are ideal.

PI [name] has a long-standing collaboration with [name], a biostatistician with MICHRS, and he has published papers, served on graduate student MS committees and taught in courses with [name]. Statistical aspects of this project can be handled through this collaboration. PI [name] has also collaborated with [name] chronic pain group, [name] mechanical engineering group and movement science groups in the School of Kinesiology. Any and all of these collaborations can be brought to bear on this project to move it forward with scientific rigor and state-of-the-art methods.

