Funds are being requested to purchase software to analyze tooth and bite splint wear, which are critical for evaluating tissue health, compliance and functional efficacy. The prices reflect large academic price reductions. Laboratory fees are needed for fabrication of the Michigan bite splints necessary for the "gold standard" control group of subjects. The microscope provides an essential and inexpensive means of quality-screening the microwear on stone models before they are shipped for analysis with the confocal microscope (see Other Expenses, below). The use of an inexpensive microscope in the [name] laboratory will effectively reduce the costs of the latter analysis by over \$2000, thus reducing budget costs by at least \$1700.

Other software as well as dental and technical supplies (> \$19,000 worth), which are necessary for successful completion of the project, will be purchased through other funding sources.

Other Expenses

Subject fee expenses have been calculated as \$20 per visit. As Fig. 1 shows, we estimate that 70 subjects will finish the first appointment. After accounting for dropouts, we estimate that 64 will finish the next two appointments. Hence the fees are calculated as shown on the budget page.

Confocal microwear processing fees are requested. These fees reflect a negotiated \$45 / subject rate, and since these microwear processing can be done after other analyses, we can target only those 58 subjects that will be included in the final analysis (Fig. 1, bottom). The processing is necessary to evaluate and fulfill the compliance and functional efficacy aspects of the project.

Indirect costs have been figured based on the modified total direct cost rate (i.e., less equipment) and at 8% as per Delta Dental Foundation's ICR.

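### For about 70 subjects and four matching factors, minimisation would balance the arms better than crossed stratification, and the four factors should be in the analysis model in all cases

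*Combined protocol and SAP*

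**What the plan says.** Section 3.1 sets the aim: "Care will be taken to match the randomized groups for age, ethnicity, gender and TMD signs/symptoms". The next sentence gives a fallback: "Alternatively these will be modeled as nuisance variables if attrition rates create bias and/or there is a lack of sufficiently sized screening pools". Section 3.2.1 says that subjects who meet the criteria are assigned to the two groups "using stratified randomization procedures". It does not list the stratification factors, their levels or cut-points, or the block size.

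On numbers, section 3.1 states "Two groups times 29 subjects per group equals 58 total needed for analysis". Section 5 (Other Expenses) says "we estimate that 70 subjects will finish the first appointment" and "we estimate that 64 will finish the next two appointments". The text does not state how many are randomised.

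On timing, section 4 says "Accounting for lag times involved in stratified randomization, enrollment will probably lag by 1-4 months". It does not say what causes the lag.

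**The concern.** Stratified blocks balance a factor only as far as the blocks fill. Crossing four factors in a trial of this size spreads subjects over many cells, and each unfilled block can leave its stratum uneven. Those remainders add up across strata, both in arm size and in the margins of age, ethnicity, gender and TMD status. The plan relies on matched groups, so the method should be one that delivers the match at this sample size.

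The plan's answer to failed matching is modelling, but only as an alternative, under two conditions with no stated threshold. The analyses named in sections 3.2.5b and 3.2.5c (ANOVA, repeated measures ANOVA or other suitable methods) list no covariates. Whether to adjust would therefore be decided once problems have appeared. At stake are some precision and a clearly pre-specified analysis.

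**Working it through.** **The plan's own figure.** Section 3.1 gives means of 3.97 and 4.45 episodes per hour (difference 0.48), SD 0.63 and alpha 0.05 (taken as two-sided). The 0.8 labelled beta is read as power. The normal formula is n = 2(1.960 + 0.842)² × 0.63² / 0.48² = 27.04, so 28 per group. With the t distribution, power is 79.95% at 28 and 81.4% at 29. The stated 29 per group is reproduced and is not in dispute.

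**Stratum size.** The 70 finishing the first appointment stand in for the number randomised. Numbers of levels are assumptions.

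| Assumed levels (age × ethnicity × gender × TMD) | Strata | Mean per stratum | Strata with fewer than 4 subjects |
|---|---|---|---|
| 2×2×2×2 | 16 | 70/16 = 4.4 | 36-51% |
| 3×3×2×2 | 36 | 70/36 = 1.9 | 80-87% |
| 3×4×2×3 | 72 | 70/72 = 1.0 | 92% |

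In the first two rows, the lower and upper figures come from equal and uneven factor frequencies (in the first row equal gives 36% and uneven 51%; in the second, equal gives 87% and uneven 80%). Only uneven frequencies were run for 72 strata.

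**Balance by method.** 2,000 trials of 70 subjects were simulated for each of five scenarios (16 and 36 strata with equal and uneven frequencies, 72 uneven), with independent factors. The uneven frequencies were, for example, 65% female and 70-80% in the largest ethnic group. Marginal imbalance is the mean absolute difference between arms within a factor level, averaged over the four factors. Ranges run across scenarios.

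| Method | Mean marginal imbalance (subjects) | Mean arm-size difference (subjects) |
|---|---|---|
| Simple randomisation | 3.8-4.7 | 6.5-6.8 |
| Unstratified blocks of 4 | 3.0-3.4 | 0.6-0.7 |
| Four-factor strata, blocks of 4 | 2.0-2.9 | 2.7-4.5 |
| Four-factor strata, blocks of 2 | 1.6-2.2 | 2.1-3.8 |
| Minimisation, probability 0.8 | 1.3-1.4 | 1.0-1.3 |

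A second, separate simulation agreed. It gave 2.1-2.8 against 1.3-1.4 for marginal imbalance. For arm size it gave 2.8-4.8 against 0.9-1.2, so the range for four-factor strata with blocks of 4 is quoted as 2.7-4.8.

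**What it costs in precision.** The efficiency lost to unequal arms is (difference/N)². A difference of 2.7 costs (2.7/70)² = 0.15%, and 4.8 costs (4.8/70)² = 0.47%. Imbalance on the factors matters more. If they explain a quarter of the outcome variance (an assumption), minimisation gives a true standard error 0-8% smaller than four-factor blocks of 4 when the analysis is unadjusted, and little difference when it is adjusted.

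**What adjustment costs.** Main effects for the four factors use 1+1+1+1 = 4 degrees of freedom at 2×2×2×2, 2+2+1+1 = 6 at 3×3×2×2 and 2+3+1+2 = 8 at 3×4×2×3. With 58 analysed in two groups, the residual degrees of freedom fall from 56 to between 48 and 52.

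**The case against.** The scheme examined here is partly inferred. Section 3.2.1 does not say that all four factors of 3.1 are crossed, and the levels, frequencies and block size above are assumptions. That stands, and the figures are conditional on it. In the most favourable case, with every factor binary and evenly split, only about a third of strata are too small to fill one block of 4.

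The loss of efficiency from unequal arms is trivial, and section 3.1 already names a modelling fallback. Both points stand, and they limit the weight of the concern. The fallback does not remove it, because it is conditional and has no stated trigger. Section 5 requests no personnel costs and relies on students, so an operator for each allocation is a real demand.

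Four stronger readings are tempting, and the evidence does not support them:

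- A reader might infer that strata this thin balance nothing. The simulation shows otherwise: four-factor blocks of 4 beat both simple and unstratified block randomisation on marginal balance in every scenario.
- A reader might infer that stratifying on gender and TMD alone would serve as well as minimisation. It improves those two factors (1.0-1.2), but leaves age and ethnicity at 2.3-3.5, against 2.0-2.6 with four-factor blocks.
- A reader might infer from the lag that subjects wait for a matched partner, so that the second allocation of a pair is known. The documents describe no pairs and no holding. Section 3.1 speaks of matching groups.
- A reader might infer that another method would abolish the lag. Its cause is not given, so this cannot be shown. The sum 14 + (1 to 4) + 6 = 21 to 24 months is tight, but section 4 already allows for the lag within its two years.

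**Conclusion.** The concern holds as a method improvement. If the four factors are crossed, stratified randomisation of about 70 subjects leaves many strata too small to fill a block of 4: about a third to a half with 16 strata, and most with 36 or more. Minimisation at probability 0.8 on the same factors cuts mean marginal imbalance from 2.0-2.9 to 1.3-1.4 subjects and mean arm-size difference from 2.7-4.8 to 1.0-1.3, with no extra subjects. The gain in precision is small to modest without adjustment and slight with it.

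The direction was the same in every scenario tried. The sizes rest on 70 as a proxy for the number randomised, on independent factors, and on assumed levels, frequencies and block size. The planned scheme does not invalidate the trial, and nothing here shows bias in the comparison. The lack of a stated scheme and the conditional adjustment should be corrected whichever method is chosen.

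**What to change.** - **Section 3.2.1:** replace stratified randomisation with minimisation on age, ethnicity, gender and TMD signs/symptoms. Define the levels of each factor and include a random element (for example, preferred arm with probability 0.8). The collaborating biostatistician should run it, concealed from enrolling staff, and release each allocation once eligibility is confirmed. State that no eligible subject is held for a match.
- **Section 3.1:** include the four factors in the analysis model in all cases, not only if attrition or small screening pools cause trouble.
- **Section 4:** explain the 1-4 month lag attributed to stratified randomisation, or revise it.

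The cost is about a paragraph of text, 4 to 8 degrees of freedom under the levels assumed above, and an operator at each enrolment. Minimisation is also partly predictable to anyone who knows the earlier allocations, which is why the random element and the concealment are needed.

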1. OVERVIEW AND OBJECTIVES

The **long-term objectives** of this research are to perform large-scale randomized clinical trials (RCT) with SISU mouth guards and SOVA night guards. Towards these long-term ends, the present proposal represents investigations into the most immediate issues that can be addressed in a preliminary study. The **outcome variables** for the present study fall into four categories: (1) fabrication efficacy, (2) compliance, (3) functional efficacy, and (4) user satisfaction. The **immediate goals of this preliminary proposal** will: (1) focus on the SOVA night guard, (2) conduct *in vivo* tests of the SOVA device under controlled clinical conditions, and (3) evaluate compliance and functional efficacy in the 'natural' environment of the patient's home. The clinical application involves protection of dental structures during nocturnal parafunction (sleep bruxism). Because of the potential co-morbidity of bruxism with temporomandibular disorders (TMD), a triad of masticatory myalgia, TM joint noises and/or joint arthritides, TMD signs and symptoms will be considered in future studies. **Future goals** will involve pursuing funding to perform large-scale RCT with both the SISU and SOVA night guards.

Specific Aim 1. Compare the SOVA night guard to the custom-acrylic bite splint in clinical laboratory conditions. Hypothesis: There will be no significant differences between the devices in terms of fabrication efficacy, functional efficacy or user satisfaction.

Specific Aim 2. Compare the SOVA night guard to the custom-acrylic bite splint under ecologically relevant conditions, i.e., the home environment. Hypothesis: There will be no significant differences between the devices in terms of compliance or functional efficacy.

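### The balancing factors enter the model only under an undefined trigger; they should be pre-specified covariates whatever the attrition

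*Combined protocol and SAP*

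**What the plan says.** Section 3.1 states: "Care will be taken to match the randomized groups for age, ethnicity, gender and TMD signs/symptoms". The next sentence gives the only rule on modelling these factors: "Alternatively these will be modeled as nuisance variables if attrition rates create bias and/or there is a lack of sufficiently sized screening pools". Section 3.2.1 assigns subjects "using stratified randomization procedures" but does not list the strata; that they are the four factors of Section 3.1 is an inference.

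The named analyses do not settle the matter. Section 3.2.5b says: "Volumetric indices will be compared between devices via ANOVA or appropriate statistical methods". Section 3.2.5c is similarly open for tissue health. Neither names or excludes covariates. No model is given for bruxism episodes per hour, the outcome behind the sample size. That the default is unadjusted is therefore read from the fallback sentence itself.

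On timing, Section 4 says that preliminary analyses "will begin as soon as data are available (approximately mid-Fall of year 1) in order to assure that experimental procedures are ideal". On attrition, Section 5 (Other Expenses) says "we estimate that 70 subjects will finish the first appointment", with 58 in the final analysis. Specific Aim 2 in Section 1 sets the hypothesis as: "There will be no significant differences between the devices in terms of compliance or functional efficacy". Aim 1 is worded in the same way.

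**The concern.** There are two problems.

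First, when arms are balanced on a factor that predicts the outcome, the variance due to that factor largely drops out of the true error of the difference between arms. A test that omits the factor still counts that variance in its estimated error. The reported standard error is then too large, the confidence interval too wide and the test conservative. In most trials that works against the investigator. Here the hypotheses are of no significant difference, so it works in their favour.

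Second, the trigger has no threshold and no decision time. Attrition is known only after follow-up. The trigger could be judged without looking at outcomes, and Section 4 ties the early analyses to checking procedures. Even so, nothing in the plan stops the choice between models being made with results in view.

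**Working it through.** **1. The plan's own sample size.** Inputs from Section 3.1: means 3.97 and 4.45, so the difference is 4.45 − 3.97 = 0.48; SD 0.63; alpha 0.05. The stated beta of 0.8 is read as 80% power. Sidedness is not stated; two-sided is assumed because one-sided gives 22.

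- Normal approximation: n = 2 × (1.96 + 0.842)² × 0.63² / 0.48² = 27.04, so 28 per group.
- Exact t test: 28.04, so 29 per group. Power at 29 is 81.4%. The stated 29 reproduces.

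**2. The limiting case of exact balance.** Let R² be the share of outcome variance that the four factors explain.

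- Reported SE = 0.63 × √(2/29) = 0.1654.
- True SE = 0.1654 × √(1 − R²).
- Type I error = 2 × [1 − Φ(1.96/√(1 − R²))].
- Unadjusted power ≈ Φ[(0.48 − 1.96 × 0.1654)/true SE].

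At R² = 0.2 the true SE is 0.148, type I error is 2.8% and unadjusted power is 85.4%. The adjusted t test, with four degrees of freedom spent, has 88.9% power. Real balance is looser than this, so step 3 relaxes it.

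**3. Simulation with imperfect balance** (60,000 trials per scenario). 70 subjects are randomised (the Section 5 figure, taken as the number randomised) in permuted blocks of 4 within strata, with random loss to 58. SD is 0.63 and the difference 0.48. The comparison is a t test on arm alone against arm plus main effects.

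Assumed, because the plan does not say: age normal, cut at the median for strata but fitted as continuous; gender 65/35; TMD present/absent 40/60; ethnicity 70/30, or 70/15/10/5 in four levels; R² shared equally by the factors. Entries are for R² = 0 / 0.1 / 0.2 / 0.3.

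| Scenario | Unadjusted SE, reported ÷ true | Type I, unadjusted | Power, unadjusted | Power, adjusted |
|---|---|---|---|---|
| (1) Ethnicity 2 levels, all four factors as strata | 0.999 / 1.029 / 1.062 / 1.097 | 0.051 / 0.044 / 0.037 / 0.031 | 0.810 / 0.817 / 0.824 / 0.831 | 0.797 / 0.837 / 0.877 / 0.915 |
| (2) Ethnicity 4 levels, all four as strata | 1.001 / 1.024 / 1.049 / 1.075 | 0.051 / 0.045 / 0.040 / 0.035 | 0.813 / 0.818 / 0.823 / 0.828 | 0.784 / 0.826 / 0.866 / 0.907 |
| (3) Ethnicity 2 levels, strata gender and TMD only | 1.001 / 1.020 / 1.041 / 1.064 | 0.050 / 0.046 / 0.042 / 0.038 | 0.813 / 0.818 / 0.823 / 0.828 | 0.794 / 0.835 / 0.874 / 0.913 |
| (4) Ethnicity 4 levels, strata gender and TMD only | 1.000 / 1.020 / 1.042 / 1.065 | 0.050 / 0.045 / 0.040 / 0.037 | 0.809 / 0.813 / 0.819 / 0.825 | 0.776 / 0.816 / 0.858 / 0.900 |

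Monte Carlo error is about 0.001 for type I error and 0.002 for power.

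- Chance of a non-significant result (1 − power) at R² = 0.1 / 0.2 / 0.3 in scenario (1): 18.3 / 17.6 / 16.9% unadjusted against 16.3 / 12.3 / 8.5% adjusted. In scenario (4): 18.7 / 18.1 / 17.5% against 18.4 / 14.2 / 10.0%.
- Mean 95% half-width with two-level ethnicity: 0.331 unadjusted against 0.320 / 0.302 / 0.283 adjusted.
- Cost at R² = 0: 0.810 − 0.797 = 1.3 points in (1) and 0.813 − 0.794 = 1.9 points in (3); 2.9 points in (2) and 3.3 points in (4).
- Adjustment gains power once R² exceeds about 0.04 to 0.05 with two levels of ethnicity, or 0.08 to 0.10 with four (separate run, 40,000 trials).

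**4. What the missing threshold decides.** Read the trigger as baseline imbalance in any factor among completers. Across scenarios (1) to (4) it fires in 46.9 / 59.6 / 61.1 / 61.4% of trials at a standardised difference above 0.25, and in 5.0 / 10.9 / 18.9 / 19.0% at p < 0.10. Both thresholds are assumed. At R² = 0.2 in scenario (1), power is 0.849 and 0.827 under these two rules, against 0.877 if the model always adjusts.

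**5. Late choice.** If either model may be reported, type I error is 5.9–6.0% in (1), 6.2–6.4% in (2), 6.0–6.6% in (3) and 6.3–6.6% in (4).

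**The case against.** The best case against has five parts.

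- **No unadjusted default is written down.** The open wording on methods would allow covariates, and the strata are not listed. This is true. But the fallback sentence makes modelling the exception, and the result survives when only gender and TMD status are strata.
- **R² is unsupported.** The plan gives no association between these factors and bruxism episodes per hour; the nearest is tooth-wear prevalence rising with age (Section 2), a different outcome. If R² is near zero, adjustment takes the one powered outcome slightly below 80%. With four-level ethnicity and R² = 0.1 the gain can be nil (0.813 to 0.816). This stands, and it is why the fix fixes ethnicity at two levels.
- **Little is lost in absolute terms.** Unadjusted power does not fall as R² rises; it goes from 81% to 83%. The defect is mainly an over-large reported standard error and a gain forgone. This stands.
- **The trigger rates are not rates of attrition bias.** The simulation loses subjects at random, so it measures chance imbalance under thresholds the plan does not state. The screening-pool trigger was not simulated. This stands: the rates show only that the text does not determine the model.
- **The wider freedom is the missing outcome model in a preliminary study.** Fixing covariates does not supply that model, and only one outcome at one time point was simulated, although functional efficacy is assessed at one week and four months. This limits the claim but does not argue for keeping an undefined switch.

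**Conclusion.** The concern holds. The plan balances on four factors, models them only under a trigger with no threshold or decision time, and leaves the model open until after outcomes are known.

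The size is moderate and conditional. For R² between 0.1 and 0.3 the unadjusted standard error is 2–10% too large and type I error is 3.1–4.6% in place of 5%. With two-level ethnicity, adjustment cuts the chance of missing a true difference of 0.48 by about 2 points at R² = 0.1 and by about 8 points at R² = 0.3. At R² = 0 it does slight harm. The late choice alone adds little to type I error.

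The sample size of 29 per group stands. Adjustment also does not make a non-significant result evidence of equivalence; that is a separate weakness of the hypotheses. The figures rest on the assumed R² range, covariate distributions and strata, on 70 being the number randomised, and on loss at random.

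**What to change.** Replace the conditional sentence in Section 3.1 with:

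> *Comparisons between devices on continuous outcomes, including bruxism episodes per hour, will include the factors used to stratify or match as main-effect covariates (age as continuous; gender; TMD joint noises or masticatory myalgia present or absent at screening; ethnicity in two levels fixed before the first randomisation), whatever the attrition or observed balance. The unadjusted comparison is a sensitivity analysis.*

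The present/absent coding of TMD status follows a distinction Section 3.1 already draws: "The presence or absence of TMD joint noises or masticatory myalgia will be permitted". Tissue health (compared with baseline, scale not stated) and single box-scale or forced-choice items are outside this sentence, and no gain is claimed for them.

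No new data are needed. TMD status is assessed at screening (Section 3.2.1), and age, ethnicity and gender must be recorded to do the matching. The price is 4 of the 56 residual degrees of freedom (6 with four-level ethnicity). If the factors explain nothing, power for 0.48 falls from 81.0–81.3% to 79.4–79.7% with two levels, or from 80.9–81.3% to 77.6–78.4% with four.
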